**NIT-110 (KEYNOTE PNA60)**  
**V7.0 incorporating Amendment 6, 26Oct2023**

## 8. Dosing Delays/ Dose Modifications

The National Cancer Institute (NCI) CTCAE Version 5.0 will be used to grade AEs. Subjects enrolled in this study will be evaluated clinically and with standard laboratory tests before and at regular intervals during their participation in this study as specified in this section.

Subjects will be evaluated for AEs (all grades), SAEs, and AEs requiring study drug dose modification, interruption, or discontinuation at each study visit for the duration of their participation in the study.

### 8.1. Dose Modification of NT-I7

Clinical experience has demonstrated that development of autoimmune inflammatory conditions is a general risk with therapeutics intended to enhance anti-tumor T-cell responses. Such irAEs have been described for virtually all organ systems and include, but are not limited to, colitis, hepatitis, pneumonitis, endocrinopathy, ocular toxicity, pancreatic toxicity, and rash.

Risks of autoimmunity associated with NT-I7 are theoretical and yet not fully evaluated in the clinical setting. Due to this potential risk of NT-I7 to induce autoimmune conditions, subjects with a history of autoimmune disease will be excluded from this study.

The risk of development of autoimmune inflammatory condition related to NT-I7 seems relatively low. None of the irAEs were reported in previous clinical studies with rhIL-7, or with NT-I7 including the FIH study completed in normal healthy individuals, and solid tumor subjects (Study No. GX-I7-HV-001 and Study No. GX-I7-CA-003).

Nevertheless, however, given the limited clinical experience with NT-I7, immune-related toxicities associated or possibly associated with NT-I7 should be closely monitored and carefully managed according to standard medical practice (e.g., thyroid hormone replacement for autoimmune hypothyroidism). Additional tests, such as autoimmune serology or biopsies, should be used to determine a possible immunogenic etiology. Although most irAEs observed with immune modulatory agents have been mild and self-limiting, such events should be recognized early and treated promptly to avoid potential major complications ([69](#)).

Discontinuation of NT-I7 may not have an immediate therapeutic effect, and there is no available antidote for NT-I7. The primary approach to mild irAEs (Grades 1–2) is supportive and symptomatic care. In severe cases, irAEs may be acutely managed with systemic corticosteroids, mycophenolate or TNF- $\alpha$  antagonists ([40](#), [69-85](#)).

Dose modifications of NT-I7 for Adverse Events: AEs from NT-I7 are expected to be mild and infrequent, transient and Grade 2 or less (as noted in the AE list, Section [11.1.1](#)). If a subject experiences a clinically significant and/or unacceptable toxicity, dosing should be interrupted, or reduced or discontinued (see below for detailed guidance), and supportive therapy administered per standard clinical practice.

A maximum of 2 dose reductions will be allowed for an individual subject. If the second dose reduction is not tolerated, study treatment should be permanently discontinued, and the subject should be followed up for safety (see Section [11.3.1](#)). The lowest dose that may be administered is:

- NT-I7 480  $\mu$ g/kg Q6W

For a Grade 1 AE, no dose modification is needed. Increase monitoring of clinical signs/symptoms and laboratory assessments as needed and treat each of the toxicities per standard of care and/or institutional guidance. For Grade 1 AE of myasthenia gravis, NT-I7 treatment may be withheld until resolved (see Section [8.1.1](#) for criteria to resume treatment) or discontinued permanently.

For a Grade 2 AE related to NT-I7, withhold administration of NT-I7 until the AE is resolved to  $\leq$  Grade 1 (see Section [8.1.1](#) for criteria to resume treatment), then resume at the same dose level.

For a Grade  $\geq 3$  AE related to NT-I7, if it is a 1st appearance, withhold administration of NT-I7 until the AE is resolved to  $\leq$  Grade 1 (see Section [8.1.1](#) for criteria to resume treatment), then decrease one dose level (e.g., to 960  $\mu\text{g}/\text{kg}$  IM Q6W if the last dose level prior to the AE was 1200  $\mu\text{g}/\text{kg}$  IM Q6W, or to 480  $\mu\text{g}/\text{kg}$  IM Q6W if the last dose level prior to the AE was 960  $\mu\text{g}/\text{kg}$  IM Q6W); if it is a 2nd appearance, withhold administration of NT-I7 until the AE is resolved to  $\leq$  Grade 1, then decrease one dose level (e.g., to 480  $\mu\text{g}/\text{kg}$  IM Q6W if the last dose level prior to the AE was 960  $\mu\text{g}/\text{kg}$  IM Q6W). The lowest dose that may be administered is 480  $\mu\text{g}/\text{kg}$  IM Q6W. Dose re-escalation to a higher dose level, up to 1200  $\mu\text{g}/\text{kg}$  IM Q6W, is allowed after being discussed with and approved by the Medical Monitor and the Sponsor.

For any grade of myocarditis, permanently discontinue NT-I7 treatment.

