#### 2.4.1.3. Benefits and Risks Conclusions

Safety, pharmacodynamic, and PK data for NT-I7 are available from one completed study in healthy volunteers, four completed studies in cancer patients, and 11 ongoing studies in patients with cancer and COVID-19. Based on these limited data, it can be concluded that:

- NT-I7 was well tolerated in healthy volunteers and adult subjects with cancer
- NT-I7 was generally well tolerated in combination with CPI in adult patients with relapsed/refractory (R/R) solid tumors. Myocarditis has been added as a potential risk for NT-I7 due to two fatal events when combined with pembrolizumab and atezolizumab, respectively. Myocarditis has an established association with both CPIs, and both patients had pre-existing cardiac risk factors; these may be more likely contributors to the events, but a causal relationship with NT-I7 cannot be ruled out.
- NT-I7 was slowly absorbed and eliminated, resulting in a flat PK profile, regardless of route of administration

- IM administration of NT-I7 resulted in more rapid absorption and had higher exposure to NT-I7 than did SC administration
- NT-I7 led to a dose-dependent increase in CD4+ and CD8+ T cells (naïve T cells, TEM, TCM, TEMRA) and NK cells, but there was no dose-dependent increase in B cells
- IM administration of NT-I7 resulted in a more pronounced increase in lymphocytes over SC administration

The anti-tumor activity observed with NT-I7 as monotherapy or in combination with other anti-cancer agents, the well-tolerated safety profile seen in humans and the unique ability of NT-I7 to increase lymphocyte counts support further clinical investigation in patients with lymphopenia, including subjects with cancer who are often lymphopenic due to either the underlying diseases or prior anti-cancer treatments.

Based on the evaluation of the cumulative safety data available and the anticipated efficacy/ benefit information for NT-I7, the benefit-risk balance for the product remains favorable.

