## 8.2. Dose Modification of Pembrolizumab

The toxicity of pembrolizumab could be accentuated by administration of NT-I7 and the component attributable to pembrolizumab and NT-I7 will be difficult if not impossible to sort out. Thus, the management of pembrolizumab will be used for the treatment of any AE. NT-I7 treatment will be discontinued when pembrolizumab must be **permanently discontinued**.

AEs associated with pembrolizumab exposure may represent an immune-related response. These irAEs may occur shortly after the first dose or several months after the last dose of pembrolizumab treatment and may affect more than one body system simultaneously. Therefore, early recognition and initiation of treatment is critical to reduce complications. Based on existing clinical study data, most irAEs were reversible and could be managed with interruptions of pembrolizumab, administration of corticosteroids and/or other supportive care. For suspected irAEs, ensure adequate evaluation to confirm etiology or exclude other causes. Dose modification and toxicity management guidelines for irAEs associated with pembrolizumab are provided in [Table 4](#).

When study interventions are administered in combination, attribution of an adverse event to a single component is likely to be difficult. Therefore, while the investigator may attribute a toxicity event to the combination, to NT-I7 alone, or to pembrolizumab alone, for adverse events listed in [Table 4](#), both interventions must be held according to the criteria in .

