### *Restarting Study Interventions:*

Subjects may not have any dose modifications (no change in dose or schedule) of pembrolizumab in this study, as described in [Table 4](#).

If the toxicity does not resolve or the criteria for resuming treatment are not met, the subject must be discontinued from all study interventions.

If the toxicities do resolve and conditions are aligned with what is defined in [Table 4](#), the combination of NT-I7 and pembrolizumab may be restarted at the discretion of the investigator. In these cases where the toxicity is attributed to the combination or to NT-I7 alone, re-initiation of pembrolizumab as a monotherapy may be considered after communication with and agreement by the Sponsor.

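### Protocol Section 8.1 stops NT-I7 permanently for any myocarditis, while Section 8.2 with Table 4 permits the combination to be restarted after a Grade 2 or first Grade 3 event, and nothing says which prevails

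*Protocol*

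**What the plan says.** Section 8.1 of the Protocol covers NT-I7. After its general grade-based rules it closes with a rule specific to one event: "For any grade of myocarditis, permanently discontinue NT-I7 treatment".

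Section 8.2 covers pembrolizumab but reaches further. It explains that toxicity can hardly be attributed to one drug or the other, and concludes that "the management of pembrolizumab will be used for the treatment of any AE". It then links the two drugs in three ways:

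- Stopping: "NT-I7 treatment will be discontinued when pembrolizumab must be" permanently stopped.
- Holding: for events listed in Table 4, "both interventions must be held according to the criteria in" a reference that is blank in the text supplied, presumably Table 4 itself.
- Restarting: if the toxicity resolves and the Table 4 conditions are satisfied, "the combination of NT-I7 and pembrolizumab may be restarted at the discretion of the investigator". For events put down to NT-I7, by itself or jointly with pembrolizumab, the section adds that "re-initiation of pembrolizumab as a monotherapy may be considered after communication with and agreement by the Sponsor".

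Table 4 as supplied has no row for myocarditis. Its catch-all row for other irAEs withholds pembrolizumab above Grade 1 and stops it permanently for recurrent Grade 3 or Grade 4. Section 11.4 lists myocarditis, whatever its grade, among the autoimmune or immune-related conditions of special interest.

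Section 2.4.1.3 reports two fatal myocarditis events with NT-I7 plus a checkpoint inhibitor, one with pembrolizumab and one with atezolizumab. It points to the known checkpoint-inhibitor association and to cardiac risk factors in both patients as more likely contributors, but adds that "a causal relationship with NT-I7 cannot be ruled out".

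**The concern.** Two parts of one protocol address what happens to NT-I7 after myocarditis. One is an absolute stop; the other is a general permission to restart the combination, which includes NT-I7. Neither refers to the other. The only sentence that speaks to scope, in Section 8.2, points towards the pembrolizumab rules.

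The myocarditis rule was changed deliberately. The Protocol Revisions entry for version 7.0 attributes the Section 8.1 change to the two deaths, and separately records that Section 8.2 and its tables were updated to match the pembrolizumab brochure. The current text does not join the two. A site that works from Section 8.2 and Table 4 could give NT-I7 again after an event that Section 8.1 treats as a permanent stop. Sites could also handle the same event differently.

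**Working it through.** No figure in the plan bears on this point and no calculation applies. The check is a comparison of the texts.

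**Which rule does myocarditis reach in Section 8.2?** Section 11.4 treats it as immune-related. The note after Table 4 takes events that are not immune-related out of the table, and Section 10 waives the guidance for events judged unrelated to pembrolizumab. So the route through Table 4 is open only for an immune-related myocarditis considered related to pembrolizumab. With no row of its own, such an event falls in the catch-all row.

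**What do the two routes give, by grade?** The catch-all row's permanent-stop entry is read here as recurrent Grade 3, or any Grade 4.

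| Myocarditis | Section 8.1, NT-I7 | Section 8.2 with the catch-all row | Result |
|---|---|---|---|
| Grade 1 | Permanent stop | No entry; the row starts above Grade 1 | Silence in the table |
| Grade 2 | Permanent stop | Withhold; combination may restart on resolution | Conflict |
| Grade 3, first | Permanent stop | Withhold; combination may restart on resolution | Conflict |
| Grade 3, recurrent | Permanent stop | Pembrolizumab stopped permanently, and NT-I7 with it | Agreement |
| Grade 4 | Permanent stop | Pembrolizumab stopped permanently, and NT-I7 with it | Agreement |

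If the entry were instead read as recurrence at either grade, a first Grade 4 event would join the conflict rows.

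**Does another passage settle precedence?**

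- Section 8.1.1 lists exceptions to the NT-I7 resume criteria. Myocarditis is not among them.
- Section 6.4.1 refers to toxicities that require permanent discontinuation, but cites only Section 8.2. The myocarditis rule sits in Section 8.1.
- Footnote 30 of the Schedule of Assessments (Section 7.4) suspends dosing while suspected myocarditis is investigated. It does not say what follows for either drug if myocarditis is confirmed, and does not cite Section 8.1.

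No sentence gives either section priority.

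**Does treating Section 8.1 as an exception close the gap?** It settles NT-I7. It leaves pembrolizumab unclear in one case: the monotherapy option is written for toxicity attributed to the combination or to NT-I7 alone. For myocarditis attributed to pembrolizumab alone, the restart text describes only the combination, which Section 8.1 would bar.

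**The case against.** The strongest reply is that both texts can be obeyed. Section 8.1 is specific to the event and to the drug, and a specific prohibition is ordinarily read as an exception to a general permission. Section 8.2 is headed as a pembrolizumab section, Table 4's action column concerns pembrolizumab, and the restart is only permitted. An investigator who never gives NT-I7 again after myocarditis breaches nothing. The trigger in Section 8.2 for stopping NT-I7 is not said to be the only one. All of this stands, and it means that the protocol nowhere orders a restart. It does not remove the problem, because the protocol leaves the reader to supply the exception while its own scope sentence points the other way.

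The second reply concerns the table. The extracted Table 4 is visibly damaged: some action cells are blank and the severe skin reaction entry appears twice. The restart permission depends on Table 4's conditions. If a lost myocarditis row required permanent discontinuation of pembrolizumab, Section 8.2 would stop NT-I7 as well, and the conflict would vanish at the grades covered by that row. This also stands. A reader might infer that the conflict holds whatever the table contains, or that the protocol gives no pembrolizumab action for myocarditis. The documents as supplied support neither inference.

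Third, there are other safeguards: the footnote 30 work-up, expedited reporting of myocarditis at any grade under Sections 11.3 and 11.4, and the Section 7.2 requirement to discuss immediate safety concerns with the sponsor. They make an unnoticed restart less likely, but none states the final action for each drug.

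**Conclusion.** The protocol is wrong as written on this point. It is an internal inconsistency rather than a design choice. The conflict is confined to Grade 2 and first Grade 3 myocarditis that is immune-related and considered related to pembrolizumab. There, Section 8.2 with Table 4 permits a restart of NT-I7 that Section 8.1 rules out.

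This rests on two assumptions: that Table 4 has no myocarditis row requiring permanent discontinuation, and that the catch-all entry means recurrent Grade 3 or any Grade 4.

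Two further readings go too far. A reader might infer that the sections conflict at every grade. They do not: at Grade 4 and recurrent Grade 3 they agree, and silence in a pembrolizumab table at Grade 1 does not authorise NT-I7 against Section 8.1. A reader might also infer that the two deaths establish NT-I7 as the cause, or that both arose with this trial's drug pair. Section 2.4.1.3 says only that a causal role cannot be excluded, and only one death was with pembrolizumab.

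The point should be corrected because the event has been fatal and the permission to restart is explicit. No view is taken on which clinical rule is right.

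**What to change.** First check the source PDF for a myocarditis row in Table 4. Then reconcile five places in the Protocol: Section 6.4.1, the myocarditis sentence in Section 8.1, the resume criteria in Section 8.1.1, the restart text in Section 8.2, and Table 4. Each should state, or refer to, the same action for each drug after myocarditis. One sentence should say whether Section 8.1 or Section 8.2 prevails when they differ. The content of the rule is for the sponsor and its clinical advisers.

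The cost is protocol wording: a cross-reference or a table entry. Sample size, endpoints and analyses are unaffected.

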### **8.1.1. Criteria to Resume for Dosing**

Subjects may resume treatment with NT-I7 when the drug-related AE(s) resolve(s) to Grade  $\leq$  1 or baseline, with the following exceptions:

- Subjects may resume treatment in the presence of Grade 2 fatigue.
- Subjects who have not experienced a Grade 3 drug-related skin AE may resume treatment in the presence of Grade 2 skin toxicity.
- Subjects with baseline Grade 1 AST/ALT or total bilirubin who require dose delays for reasons other than a 2-grade shift in AST/ALT or total bilirubin may resume treatment in the presence of Grade 2 AST/ALT OR total bilirubin.
- Drug-related pulmonary toxicity, diarrhea, or colitis must have resolved to baseline before treatment is resumed. Subjects with persistent Grade 1 pneumonitis after completion of a steroid taper over at least 1 month may be eligible for re-initiation of study treatment if discussed with and approved by the Medical Monitor and the Sponsor.
- Subjects who received systemic corticosteroids for management of any drug-related toxicity must be off corticosteroids or have tapered down to an equivalent dose of prednisone  $\leq 10 \text{ mg/day}$ .
- Drug-related endocrinopathies adequately controlled with only physiologic hormone replacement may resume study treatment after consultation with and approved by the Medical Monitor and the Sponsor.

Prior to re-initiating study treatment in a subject with a dosing delay lasting  $> 12$  weeks (84 days) for NT-I7 or  $> 6$  weeks (42 days) for pembrolizumab, the NIT designee) must be

consulted and approves the re-initiation of study treatment. Tumor assessments should continue as per protocol even if dosing is delayed. Periodic study visits to assess safety and laboratory studies should also continue every 3 weeks or more frequently if clinically indicated during such dosing delays.

## 8.2. Dose Modification of Pembrolizumab

The toxicity of pembrolizumab could be accentuated by administration of NT-I7 and the component attributable to pembrolizumab and NT-I7 will be difficult if not impossible to sort out. Thus, the management of pembrolizumab will be used for the treatment of any AE. NT-I7 treatment will be discontinued when pembrolizumab must be **permanently discontinued**.

AEs associated with pembrolizumab exposure may represent an immune-related response. These irAEs may occur shortly after the first dose or several months after the last dose of pembrolizumab treatment and may affect more than one body system simultaneously. Therefore, early recognition and initiation of treatment is critical to reduce complications. Based on existing clinical study data, most irAEs were reversible and could be managed with interruptions of pembrolizumab, administration of corticosteroids and/or other supportive care. For suspected irAEs, ensure adequate evaluation to confirm etiology or exclude other causes. Dose modification and toxicity management guidelines for irAEs associated with pembrolizumab are provided in [Table 4](#).

When study interventions are administered in combination, attribution of an adverse event to a single component is likely to be difficult. Therefore, while the investigator may attribute a toxicity event to the combination, to NT-I7 alone, or to pembrolizumab alone, for adverse events listed in [Table 4](#), both interventions must be held according to the criteria in .

### *Holding Study Interventions:*

When study interventions are administered in combination, if the AE is considered immune-related, both interventions should be held according to recommended dose modifications.

### *Restarting Study Interventions:*

Subjects may not have any dose modifications (no change in dose or schedule) of pembrolizumab in this study, as described in [Table 4](#).

If the toxicity does not resolve or the criteria for resuming treatment are not met, the subject must be discontinued from all study interventions.

If the toxicities do resolve and conditions are aligned with what is defined in [Table 4](#), the combination of NT-I7 and pembrolizumab may be restarted at the discretion of the investigator. In these cases where the toxicity is attributed to the combination or to NT-I7 alone, re-initiation of pembrolizumab as a monotherapy may be considered after communication with and agreement by the Sponsor.

**Table 4: Dose Modification and Toxicity Management Guidelines for Immune-related AEs Associated with Pembrolizumab**

General instructions: 
Severe and life-threatening irAEs should be treated with IV corticosteroids followed by oral steroids. Other systemic immunosuppressive treatment may be considered if the irAEs are not controlled by corticosteroids.
 
The corticosteroid taper should begin when the irAE is <math>\leq</math> Grade 1 and continue at least 4 weeks.
 
If pembrolizumab has been withheld, pembrolizumab may resume after the irAE decreased to <math>\leq</math> Grade 1 after corticosteroid taper.
 
If another episode of a severe adverse reaction occurs, permanently discontinue pembrolizumab.
				
irAEs	Toxicity grade (CTCAE V5.0)	Action with pembrolizumab	Corticosteroid and/or other therapies	Monitoring and follow-up
Pneumonitis	Grade 2	Withhold	Administer corticosteroids (initial dose of 1 to 2 mg/kg prednisone or equivalent) followed by taper	Monitor subjects for signs and symptoms of pneumonitis  Evaluate subjects with suspected pneumonitis with radiographic imaging and exclude other causes. Initiate corticosteroid treatment.
	Recurrent Grade 2, Grade 3 or 4	Permanently discontinue		
Colitis	Grade 2 or 3	Withhold	Administer corticosteroids (initial dose of 1 to 2 mg/kg	Monitor subjects for signs and symptoms of colitis and exclude other causes.

	Grade 4	Permanently discontinue	prednisone or equivalent) followed by taper	
Hepatitis	Grade 2	Withhold or discontinue based on severity of liver enzyme elevations.	Administer corticosteroids (initial dose of 0.5 to 1 mg/kg prednisone or equivalent) followed by taper	Monitor subjects for changes in liver function (at the start of treatment, periodically during treatment, and as indicated based on clinical evaluation) and symptoms of hepatitis and exclude other causes.
	Grade 3 or 4		Administer corticosteroids (initial dose of 1 to 2 mg/kg prednisone or equivalent) followed by taper	
Type 1 diabetes mellitus (T1DM) or Hyperglycemia	T1DM		Initiate insulin replacement therapy for subjects with T1DM	Monitor subjects for hyperglycemia or other signs and symptoms of diabetes

	Severe hyperglycemia	Withhold until metabolic control is achieved		
Adrenal insufficiency (primary and secondary) and Hypophysitis	Grade 2	Withhold	Administer corticosteroids for adrenal insufficiency and initiate hormonal replacements as clinically indicated	Monitor for signs and symptoms of adrenal insufficiency and hypophysitis (including hypopituitarism) and exclude other causes.
	Grade 3 or 4	Withhold or discontinue		
Hyperthyroidism	Grade 2	Continue	Manage symptomatically	Monitor for changes in thyroid function (at the start of treatment, periodically during treatment and as indicated based on clinical evaluation) and clinical signs and symptoms of thyroid disorders
	Grade 3 or 4	Withhold or permanently discontinue		
Hypothyroidism	Grade 2, 3, 4	Continue	May be managed with replacement therapy without corticosteroids.	Monitor for changes in thyroid function (at the start of treatment, periodically during treatment and as indicated based on clinical evaluation) and clinical signs and symptoms of thyroid disorders
Nephritis	Grade 2	Withhold	Administer corticosteroids (prednisone 1–2 mg/kg or equivalent)	Monitor changes of renal function and exclude other causes.
	Grade 3 or 4	Permanently discontinue		

			followed by taper	
Severe skin reactions		Based on the severity of AE, withhold or permanently discontinue	Based on severity of AE, administer corticosteroids	Monitor for suspected severe skin reactions and exclude other causes. For signs and symptoms of SJS/TENS, refer the subject for specialized care for assessment and treatment.
Severe skin reactions	Suspected SJS, TEN, or DRESS	Withhold	Based on severity of AE administer corticosteroids	
	Confirmed SJS, TEN, or DRESS	Permanently discontinue	Administer corticosteroids with specialized care	
All Other irAEs	> Grade 1	Withhold	Based on severity of AE administer corticosteroids and taper upon improvement to Grade 1 or less, over at least one month.	Ensure adequate evaluation to confirm etiology or exclude other causes
	Recurrent Grade 3 or Grade 4	Permanently discontinue	Administration of other systemic immunosuppressants can be	

			considered if irAEs cannot be controlled with corticosteroid use.	
--	--	--	---	--

AE(s)=adverse event(s); ALT= alanine aminotransferase; AST=aspartate aminotransferase; CTCAE=Common Terminology Criteria for Adverse Events; DRESS=Drug Rash with Eosinophilia and Systemic Symptom; GI=gastrointestinal; IO=immuno-oncology; ir=immune related; IV=intravenous; SJS=Stevens-Johnson Syndrome; T1DM=type 1 diabetes mellitus; TEN=Toxic Epidermal Necrolysis; ULN=upper limit of normal.

